#### 9.4.3 Method of Assigning Subjects to Treatment Group

This is an open-label study. An interactive voice response system will be used to register subjects into this study. All subjects who provide signed informed consent to participate in this study and satisfy all eligibility requirements (see [Section 9.3](#)) will be assigned to receive perampanel for the Titration Period and Maintenance Period. There is no randomization in this study.

#### 9.4.4 Selection of Doses in the Study

Perampanel is approved for the treatment of POS, with or without SGS, in patients with epilepsy 4 years of age and older, and as adjunctive therapy of PGTCS, in patients with epilepsy 12 years of age and older. (revised per Amendment 01) The initial dose of perampanel will be 2 mg/day and this dose can be escalated by increments of 2 mg/day no more frequently than at weekly intervals, up to 12 mg, a maximum dose, depending on the clinical response and tolerability in subjects.

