**Table 1 Dosing Titration Schedule**

Category	Week a	Perampanel Dose (mg/day)
Required	1	2
	2	2
	3	4
	4	4
		Telephone Visit
Optional Escalation b	5	6
	6	6
		Follow-Up Telephone Call c
	7	8
	8	8
		Follow-Up Telephone Call c
	9	10
	10	10
		Follow-Up Telephone Call c
	11	12
	12	12
	13	12

a: Subjects on a concomitant enzyme-inducing antiepileptic drug may be up-titrated at 1-week intervals if needed.

b: Subjects should be titrated to 4 mg. Additional dose escalation is optional depending on subject response and tolerability, following assessment by Telephone Visit or follow-up calls.

c: If needed; investigator should follow up with subject via telephone call prior to further dose escalation.

Treatment will initially be titrated up to perampanel 4 mg based on clinical response and tolerability. Thereafter, titration will be based on the investigator’s judgment; subjects may have further dose increases in increments of 2 mg, per evaluation by the investigator (Telephone Visit 3) prior to further dose escalation. The maximum dose is 12 mg. At least 2 weeks must elapse between dose increases, with the exception of subjects who are taking any concomitant drug that shortens the half-life of perampanel (eg, phenytoin, carbamazepine, oxcarbazepine, eslicarbazepine), in which case the treatment may be up-titrated at 1-week intervals if needed. Sites must enter the perampanel dosing information

into the Interactive Response Technology (IRT) system on Weeks 2, 4, 6, 8, 10, and 12 to track subject dosing. Adjustments of the concomitant AED dose level during the Titration Period are not permitted. (revised per Amendment 01)

The perampanel dose can be down-titrated based on tolerability, at the discretion of the investigator. Subjects who cannot tolerate the 4 mg dose by the end of the Titration Period will be discontinued from the study.

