## 9.4 Treatment

### 9.4.1 Treatment Administered

Perampanel will be administered to subjects during each study period. Tablets at the assigned dose strength will be taken orally once daily before bedtime. At the beginning of the Titration Period, oral perampanel will start at a dose of 2 mg QD. Doses of perampanel will then be up-titrated in increments of 2 mg/day at no less than 2-week intervals according to the investigator's judgment. At the 4 mg dose (Week 4, telephone call, Visit 3), the investigator will confirm whether further dose escalation is needed based on subject response

and tolerability. The investigator may adjust dosing further or leave the subject at 4 mg. The maximum dose is 12 mg. Subjects who are taking concomitant AEDs that are known cytochrome P450 (CYP) enzyme inducers (eg, phenytoin, carbamazepine, oxcarbazepine, eslicarbazepine) which shorten the half-life of perampanel, can undergo up-titration in 2-mg increments at intervals of at least 1 week.

The study drug will be dispensed to each subject or guardian/legally authorized representative at Visit 2 (Week 0), Visit 4 (Week 13), Visit 5 (Week 26), and Visit 6 (Week 39). Sites must enter the perampanel dosing information into the IRT system on Weeks 2, 4, 6, 8, 10, and 12 to track subject dosing. (revised per Amendment 01)

Tablet(s) cannot be split, broken or crushed prior to administration, and should be administered whole at bedtime.

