### 5.2.3 Protocol Deviations

Subjects with major protocol deviations will be listed. These may include:

- Recruitment of a subject who did not satisfy the inclusion/exclusion criteria
- Subjects who took excluded medication
- Overdose of Investigational Products of 120% or above between 2 consecutive visits or Study Medication compliance <80% between two consecutive visits.
- Continuation of treatment with Study Medication after a treatment related withdrawal event
- Unauthorized dose adjustment during Titration Period and Maintenance Period.

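### Protocol Section 9.4.4 states a weekly escalation limit without the enzyme-inducer condition that the Synopsis, Section 9.1.2/Table 1 and Section 9.4.1 attach to 1-week steps

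*Protocol*

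**What the plan says.** **Protocol 9.4.4 (Selection of Doses in the Study).** After a 2 mg/day start, the dose may rise in 2 mg/day steps "no more frequently than at weekly intervals", to a maximum of 12 mg, depending on response and tolerability. The sentence names no subject group and does not refer to any other section.

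**Protocol 9.1.2 (Titration Period) and Table 1.** The general rule is "At least 2 weeks must elapse between dose increases". An exception covers anyone on another medicine that reduces perampanel's half-life, "in which case the treatment may be up-titrated at 1-week intervals if needed". Table 1 moves up in 2-week steps and gives the faster option only in footnote a: "Subjects on a concomitant enzyme-inducing antiepileptic drug may be up-titrated at 1-week intervals if needed". The Synopsis carries the same rule, the same exception and the same schedule.

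**Protocol 9.4.1 (Treatment Administered).** Doses rise "in increments of 2 mg/day at no less than 2-week intervals". Subjects on CYP-inducing AEDs may step up at intervals of at least 1 week.

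**SAP 5.2.3 (Protocol Deviations).** Among the items that the list of major deviations may include is "Unauthorized dose adjustment during Titration Period and Maintenance Period". The SAP does not say which protocol text decides whether an adjustment was authorized.

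**The concern.** The question arises for a subject who is not on a half-life-shortening drug, for example one on perampanel monotherapy or on a non-inducing AED. A dose increase one week after the last one is within Section 9.4.4 and outside the Synopsis, Section 9.1.2, Table 1 and Section 9.4.1.

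Two things are at stake. The first is dosing: the protocol ties escalation to tolerability, and two sections give different limits for the same subject. The second is classification: the same 1-week step would be authorized under one section and unauthorized under the others, so two people compiling the SAP 5.2.3 listing could reach different results.

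Dosing and titration are also a secondary objective, and Section 9.2.2 presents retention, the primary endpoint, as the result of satisfactory efficacy and safety. The documents give no figure linking titration speed to retention, so no effect on the endpoint is claimed here.

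**Working it through.** **Inputs**
- Start dose 2 mg/day, maximum 12 mg, step 2 mg (Sections 9.4.4, 9.4.1 and 9.1.2).
- General minimum interval 14 days (Synopsis, Sections 9.1.2 and 9.4.1); minimum interval in Section 9.4.4, 7 days.
- Telephone Visit 3 evaluation before going above 4 mg (Sections 9.1.2 and 9.4.1), scheduled at Week 4, Day 29 (Table 4), with a ±7-day visit window (Table 4, footnote b).

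**Formulas.** Number of steps = (12 − 2)/2 = 5. First day at step k = 1 + k × interval. The study week is the day divided by 7, rounded up.

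**Plan's own schedule.** With 14 days, 12 mg starts on Day 1 + 5 × 14 = 71, which is Week 11. The intermediate steps fall in Weeks 3, 5, 7 and 9. Table 1 is reproduced at every dose.

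**Section 9.4.4 read alone.** With 7 days, 12 mg starts on Day 1 + 5 × 7 = 36, which is Week 6.

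**Weekly steps with the Telephone Visit 3 evaluation kept.** The first dose above 4 mg starts on Day 29, and three further weekly steps give Day 29 + 3 × 7 = 50, which is Week 8. If the call is made 7 days early, on Day 22, the result is Day 22 + 3 × 7 = 43, which is Week 7.

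| Dose | 2-week steps (Table 1) | 9.4.4 read alone | Weekly steps, evaluation on Day 29 |
|---|---|---|---|
| 2 mg | Day 1 | Day 1 | Day 1 |
| 4 mg | Day 15 | Day 8 | Day 8 to 15 |
| 6 mg | Day 29 | Day 15 | Day 29 |
| 8 mg | Day 43 | Day 22 | Day 36 |
| 10 mg | Day 57 | Day 29 | Day 43 |
| 12 mg | Day 71 | Day 36 | Day 50 |

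Against Table 1, 12 mg comes 71 − 36 = 35 days earlier if Section 9.4.4 is read alone, and 71 − 50 = 21 days earlier if the evaluation is kept on its scheduled day.

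**Status of a 1-week increase, by section**

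| Subject | 9.4.4 | Synopsis, 9.1.2/Table 1, 9.4.1 |
|---|---|---|
| On a half-life-shortening drug | permitted | permitted |
| Not on such a drug | permitted as worded | not permitted |

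The texts differ only in the second row.

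**The case against.** **Outer bound.** The wording "no more frequently than at weekly intervals" sets a ceiling on frequency. Across the whole study the shortest permitted interval is indeed 1 week, through the inducer exception, and a site that follows Sections 9.1.2 and 9.4.1 never breaches Section 9.4.4. A reader might infer that Section 9.4.4 entitles every subject to weekly escalation, or that the sections cannot all be obeyed. The documents do not support either: the stricter text satisfies all of them. What remains is that nothing in Section 9.4.4 marks it as an outer bound, and it neither repeats the condition nor points to where it stands.

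**The 2-week rule dominates.** It appears in the Synopsis, Section 9.1.2, Table 1 and Section 9.4.1. IRT dose entry at Weeks 2, 4, 6, 8, 10 and 12 follows the same rhythm. A site would have to rely on Section 9.4.4 in isolation to be misled. This stands, and it makes the misreading less likely.

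**Halved titration time.** A reader might take Day 36 as the practical consequence. It holds only if the Telephone Visit 3 evaluation is ignored as well, and Section 9.4.4 does not waive that evaluation. About Day 50 is the fairer figure.

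**Statistical consequence.** A reader might infer that the results depend on this. The SAP defines only the Safety and Full Analysis Sets, neither of which uses deviations, and the SAP 5.2.3 items are ones that the list may include. No subject leaves the retention analysis, or any other, because of how a dose step is classified.

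**Conclusion.** Section 9.4.4 omits a condition that the other sections state, and as worded it allows a 1-week increase in a subject without an inducer that those sections bar. This is a discrepancy of wording to be reconciled. It is not a flaw in the analysis.

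The possible departure from Table 1 at 12 mg is about 3 weeks (Day 50 against Day 71) with the Day 29 evaluation kept, and 5 weeks (Day 36) on Section 9.4.4 alone. Both figures assume an increase at every permitted date up to the maximum dose, so they are upper limits on speed and do not describe expected dosing.

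SAP Section 7 says enrollment was terminated before the planned sample size was reached. The documents do not say how many subjects were still being dosed. The practical effect is therefore on any remaining dosing and on how dose changes are classified in the deviation listing. The point is worth correcting because it concerns dosing and costs very little.

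**What to change.** The clinical team should reconcile Section 9.4.4 with the Synopsis, Section 9.1.2/Table 1 and Section 9.4.1 so that one interval rule per subject group is stated, or so that Section 9.4.4 cross-refers to the place where it is stated. Which interval applies is for the clinical team; none is proposed here.

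The reconciled rule should then be used when dose changes are classified as unauthorized for the SAP 5.2.3 listing. The classification should be settled before database lock.

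The cost is a short protocol clarification and, if wanted, one cross-reference in the SAP. No analysis set, endpoint or planned summary changes.

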#### 9.4.5 Selection and Timing of Dose for Each Subject

Subjects will begin receiving perampanel 2 mg/day and be up-titrated in increments of 2 mg to a maximum dose of 12 mg, depending on the clinical response and tolerability in each subject. Subjects will start taking study drug at bedtime at Visit 2 (Week 0).

#### 9.4.6 Blinding

The study will not be blinded.

#### 9.4.7 Prior and Concomitant Drug/Therapy

- Concomitant AED for subjects who receive perampanel as a 1st adjunctive therapy

- Only 1 AED can be used.
- A concomitant AED must be used at the stable dose and administered between 8 weeks before Visit 2 (Week 0) and the end of the Titration Period. The dose and administration of the AED may be modified during the Maintenance Period based on the investigator's judgment.
- Concomitant medication  
The following concomitant drugs are prohibited throughout the study period (up to the Follow-Up Period or early discontinuation visit): (revised per Amendment 01)
  - CYP3A4-inducing drugs and food below as follows (from 30 days before Visit 1): Rifampicin, troglitazone, barbiturates except for use as AED, modafinil, efavirenz, nevirapine, glucocorticoid except for topical use, pioglitazone, rifabutin, and food containing St. John's Wort (*Hypericum perforatum*). (revised per Amendment 01)
  - Antipsychotics
  - Other investigational drugs. (revised per Amendment 01).
  - CBD products (revised per Amendment 01)Restricted concomitant drug:
  - Any changes in the dosing regimen of antidepressant or antianxiety drugs during the study must be recorded.
  - Barbiturates (except for seizure control indication and premedication for EEG) and benzodiazepines (except for seizure control indication) within 8 weeks prior to Visit 2 (Week 0)
- Concomitant therapy (revised per Amendment 01)  
Prohibited concomitant therapy  
The following therapies must not be implemented during the study:
  - Investigational deviceRestricted concomitant therapy:
  - Vagus nerve stimulation is allowed, but stimulator parameters cannot be changed for 8 weeks before Visit 2 (Week 0) or thereafter during the study.
  - A ketogenic diet will be allowed as long as the subject has been on this diet for 8 weeks prior to Visit 2 (Week 0). Additionally, a ketogenic diet cannot be newly added or discontinued during the study.Clarification of previous AED medication:
  - Subjects may switch monotherapies provided the time to complete the conversion is less than 30 days.
  - Subjects on short-term monotherapy (<2 weeks) may be eligible for the study provided they stop the initial therapy at the time of perampanel dosing.

#### 9.4.8 Treatment Compliance

Records of treatment compliance for each subject will be kept during the study. CRAs will review treatment compliance during site visits and at the completion of the study.

The importance of compliance with the treatment regimen will be emphasized at each visit. The subject must be reminded to return all unused medication from the previous treatment period and report the number of tablet(s) lost to the investigator if tablet(s) are lost. The investigator or designated study site personnel should count the number of tablets returned by the subject and investigate the number of tablet(s) lost from the subject to establish the number of tablets used, and compare this to the number of tablets expected to be used for the period. A record of this reconciliation must be maintained using the accountability forms, and any issues of non-compliance discussed with the subject.

#### 9.4.9 Drug Supplies and Accountability

In compliance with local regulatory requirements, drug supplies will not be sent to the investigator (or if regionally required, the head of the medical institution or the designated pharmacist) until the following documentation has been received by the sponsor:

- A signed and dated confidentiality agreement
- A copy of the final protocol signature page, signed and dated by both the sponsor and investigator
- Written proof of approval of the protocol, the ICFs, and any other information provided to the subjects by the IRB/IEC for the institution where the study is to be conducted
- A copy of the IRB/IEC-approved ICF and any other documentation provided to the subjects to be used in this study
- The IRB/IEC membership list and statutes or Health and Human Services Assurance number
- An investigator-signed and dated FDA Form FDA 1572, where applicable
- Financial disclosure form(s) for the PI and all subinvestigators listed on Form FDA 1572, where applicable
- A signed and dated curriculum vitae of the PI including a copy of the PI's current medical license medical registration number on the curriculum vitae
- A signed and dated clinical studies agreement
- A copy of the regulatory authority approval for the country in which the study is being conducted, and the Import License
- For US sites only: A copy of the controlled Substance Registration Certificate (DEA-Form 223), which must be current (ie, not expired) and have the appropriate controlled substance schedule listed for the study drug. Study drug will only be shipped to the exact address found on the DEA-Form 223 registration.

The investigator and the designated pharmacist will be responsible for the accountability of all study drugs (dispensing, inventory, and record keeping) following the sponsor's instructions and adherence to GCP guidelines as well as local or regional requirements.

Under no circumstances will the investigator allow the study drugs to be used other than as directed by this protocol. Study drug will not be dispensed to any individual who is not enrolled in the study, or to the guardian/legally authorized representative of an adolescent who is not enrolled in the study.

The site must maintain an accurate and timely record of the following: receipt of all study drugs, dispensing of study drugs to the subject, collection and reconciliation of unused study drugs that are either returned by the subjects or shipped to site but not dispensed to subjects, and return of reconciled study drugs to the sponsor or (where applicable) destruction of reconciled study drugs at the site. This includes, but may not be limited to: (a) documentation of receipt of study drugs, (b) study drugs dispensing/return reconciliation log, (c) study drugs accountability log, and (d) documentation of returns to the sponsor. All forms will be provided by the sponsor. Any comparable forms that the site wishes to use must be approved by the sponsor.

The study drugs and inventory records must be made available, upon request, for inspection by a designated representative of the sponsor or a representative of a health authority (eg, FDA, Medicines and Healthcare products Regulatory Agency). As applicable, all unused study drugs and empty and partially empty containers from used study drugs are to be returned to the investigator or the designated pharmacist by the subject and, together with unused study drugs that were shipped to the site but not dispensed to subjects, are to be returned to the sponsor's designated central or local depot(s) during the study or at the conclusion of the study, unless provision is made by the sponsor for destruction of study drugs and containers at the site. Destruction at the site will only occur under circumstances where regulation or supply type prohibits the return of study drugs to the central or local depot(s). Approval for destruction to occur at the site must be provided by the sponsor in advance. Upon completion of drug accountability and reconciliation procedures by the site's personnel and documentation procedures by the sponsor's personnel, study drugs that are to be returned to the sponsor's designated central or local depot(s) must be boxed, sealed, and shipped back to the central or local depot(s) following all local regulatory requirements. In some regions, study drugs may be removed from the site and hand delivered to the central or local depot by sponsor representatives. Where study drugs are approved for destruction at the site, destruction will occur following the site's standard procedures and certificates of destruction will be provided to the sponsor.

Drug accountability will be reviewed during site visits and at the completion of the study.

## **9.5 Study Assessments**

### **9.5.1 Assessments**

#### **9.5.1.1 Demographic/Baseline Assessments**

##### **9.5.1.1.1 DEMOGRAPHY**

Subject demography information will be collected at Screening Visit (Visit 1). Demography information includes date of birth (or age), sex.

#### **9.5.1.1.2      DIAGNOSIS**

The subject must have been diagnosed with epilepsy with POS (with or without SGS) or with PGTCs. To support an epilepsy diagnosis, either of the following must have occurred: at least 2 unprovoked (or reflex) seizures occurring greater than 24 hours apart, or 1 unprovoked (or reflex) seizure with EEG evidence of seizures. (revised per Amendment 01) In addition, subjects should be receiving treatment with a single AED, and need additional AED treatment or have not previously received treatment with an AED or are currently receiving monotherapy treatment (no history of AED polytherapy) and wish to switch to another monotherapy treatment.

#### **9.5.1.1.3      SEIZURE TYPE AND FREQUENCY**

Seizure type and frequency/interval from the 12 weeks preceding the 1st perampanel dose (Visit 2) will be collected by the investigator, including retrospective data collection as needed.

#### **9.5.1.1.4      MEDICAL HISTORY**

Medical and surgical history and current medical conditions will be recorded at the Screening Visit. All pertinent medical and surgical history within 5 years before the Screening Visit must be noted on the appropriate eCRF.

Vital signs including blood pressure, body temperature, respiratory rate and pulse rate will be performed as designated in [Section 9.5.1.6.4](#). Documentation of vital signs will be included in the source documentation at the site. Weight should be recorded at each visit, and height should be recorded at baseline. For subjects <18 years of age, height should also be recorded at the last Follow-Up Visit.

Prior and concomitant medications including drug name, dosage, administration route, within 24 weeks (and as long as available, for AEDs) before the Screening Visit will be recorded.

#### **9.5.1.1.5      CONCOMITANT ANTIEPILEPTIC DRUGS**

AED treatment including drug name, dosage, and administration route, will be obtained throughout the study.

#### **9.5.1.2      Efficacy Assessments**

Exposure data will be utilized to assess the primary endpoint. Secondary efficacy variables will be based on seizure frequency. Seizure frequency data will be collected in subject diaries by subjects or guardian/legally authorized representative during the study including the Titration Period and the Maintenance Period. Baseline seizure frequency data for up to 12 weeks before Visit 2 (Week 0) will be collected by subjects or guardian/legally authorized representative, retrospectively (for history prior to screening) and prospectively (during baseline). Subjects will be eligible for study enrollment after they have experienced the 2 unprovoked (or reflex) seizures occurring greater than 24 hours apart, or 1 unprovoked (or

reflex) seizure with EEG evidence of seizures, and will not need to complete the full 12-week diary to enter the Titration Period. (revised per Amendment 01) Seizure frequency data in subject diaries will be reviewed with the investigator(s) at Visit 2, 4, 5, 6, and 7. Seizure frequency from diary entries or principal investigator verification will be used to assess efficacy endpoints as appropriate. (revised per Amendment 01)

